4.2 Study Endpoints

4.2.1 Primary Study Endpoints

The primary endpoint will be the assessment of pelvic pain using the Visual Analogue Scale (VAS) at enrollment date, POD 1, POD 27, POD 55, and POD 83. The VAS is a clinically relevant, valid, and reliable measure of pain.^{28–30} Post-operative participant self-reported scores will be used to determine the efficacy of the test drug in pain management.

4.2.2 Secondary Study Endpoints

The secondary endpoints will examine short- and long-term recovery, opioid use, side effects and adverse events.

- Endometriosis Health Profile-30 (EHP-30): A Health-Related Quality of Life (HRQoL) patient self-report tool used to measure the wide range of effects that endometriosis can have on patients' lives, including work, relationship with child/children, sexual relationship, feelings about medical profession, feelings about treatment, and feelings about infertility. This report will be completed on the enrollment date, POD 1, POD 27, POD 55, POD 83. The EHP-30 will be used to measure the quality-of-life component of short- and long-term recovery.
- 2. General Anxiety Disorder-7 (GAD-7): A Self-administered 7 item instrument that uses some of the DSM-V criteria for General Anxiety Disorder to identify probable cases of GAD along with measuring anxiety symptom severity. The GAD-7 assessments will be completed on the enrollment date, POD 1, POD 27, POD 55 and POD 83. The GAD-7 will be used to measure the anxiolytic effects of the test drug.
- 3. Montgomery-Asberg Depression Rating Scale (MADRS): A 10 item questionnaire often used by psychiatrists to measure the severity of depressive episodes in patients with mood disorders. MADRS assessments will be completed on the enrollment date, POD 1, POD 27, POD 55 and POD 83. The MADRS will be used to measure the antidepressant effects of the test drug.
- 4. Douleur Neuropathique 4 Questions (DN-4): This 10 item questionarre identifies neuropathic pain, which ketamine has been shown to address. This will allow for subgroup analyses that can shed light on best practice for these patients. The DN-4 will be completed at baseline by the study physician.
- Opioid use: The opioid use and dosage assessment will be assessed through medical records and subject reports. Assessment of opiate use will be used to determine the opiate-sparing effects of the study drug. Opioid use and dosage assessments will be completed on the enrollment date, POD 0, POD 1, POD 27, POD 55, and POD 83.
- 6. Assessment of Side Effects: A questionnaire will assess any potential side effects of the intervention at POD 0, POD 1, and POD 27.

May 2, 2022 Version: 1.23

, 2022 Page 10

7. Assessment of Adverse Events: Assessment of adverse events as reported by participant or observed by investigator and study team The assessment of adverse events will be completed at the enrollment date, POD 1, POD 27, POD 55 and POD 83. Events will be recorded via study database.

5 Study Enrollment and Withdrawal

Prospective subjects will be screened, recruited, and consented prior to their surgery date. Participants will be screened during the surgical consult by the study surgeon, who may give potential participants a one-pager with key information on the study. Should the patient meet the inclusion criteria (see below) and are interested in participating, they will be referred to (their information will be shared with) a clinical research coordinator on the study team who will call prospective subjects or arrange a video conference session (WebEx only). Eligible patients will be invited to participate in the study and the research coordinator will answer any outstanding questions and begin the informed consent process.

The subject will remotely receive a link to the informed consent, sign, and return informed consent document through a REDCap link. The link to the REDCap e-consent will be submitted to the IRB via modification following initial approval. The study team will not use the REDCap e-consent until it has been IRB approved. The prospective subject will be emailed a copy of the informed consent form. Once informed consent is given, the study team member will provide the participant with information regarding the next steps for participation. Consent may be obtained up to two months before surgery at the earliest, but will occur no less than 2 days before a subject's surgery at the latest..

5.1 Inclusion Criteria

In order to be eligible to participate in this study, an individual must meet all of the following criteria:

- 1. Adults, aged 18 to 65 years old
- 2. Experiencing chronic pain, defined as experiencing moderate to severe pelvic pain for greater than 6 months
- 3. Scheduled to undergo robotic endometriosis removal surgery
- 4. Willing to comply with all study procedures and be available for the duration of the study.
- 5. Subject is medically stable.

5.2 Exclusion Criteria

An individual who meets any of the following criteria will be excluded from participation in this study:

- 1. Cognitive impairment (by history) or clinical signs of altered mental status such as confusion, amnesia, disorientation, fluctuating levels of alertness, etc. that may interference with adherence to study procedures and/or participant safety.
- 2. Past ketamine or phencyclidine misuse or abuse
- 3. Schizophrenia or history of psychosis
- 4. Known sensitivity or allergy to ketamine
- 5. Liver or renal insufficiency.
- 6. History of uncontrolled hypertension, chest pain, cardiac arrythmia, stroke, head trauma, intracranial mass or hemorrhage or pressure, glaucoma, acute globe injury, uncontrolled thyroid disease, porphyria, or any other contraindication to ketamine. Use of lamotrigine, alfentanil, physostigmine, and 4-aminopyridine are contraindicated
- 7. Pregnancy or nursing women
- 8. Currently participating in another pain interventional trial
- 9. Unwillingness to give informed consent
- 10. Non-English-speaking patients as the EHP-30 instrument has only been licensed to NYULH in English.

May 2, 2022 Version: 1.23

May 2, 2022 Page 11

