Dermatologic: Dermatologic side effects have included transient erythema and/or morbilliform rash.

Psychiatric: Psychiatric side effects have included anxiety, euphoria, dysphoria, illusions, hallucinations, flashbacks, blunted affect, catatonia, and psychotic episodes.

Neurologic: Impaired attention/memory/judgment, disorientation, delirium, diplopia, and blurred vision.

Urinary: Increased urinary output; rarely cystitis.

Duration of Effects: Onset of analgesic effect of ketamine is within 1-5 minutes if injected. The effects of ketamine generally last 30-45 minutes if injected as a single bolus. However, some residual symptoms such as nausea and vomiting may persist longer than general effects.

Drug Interactions: Benzodiazepines may decrease ketamine-associated emotional distress but does not decrease cognitive or behavioral effects of ketamine. Acute administration of diazepam increases the half-life of ketamine. Lamotrigine significantly decreases ketamine-induced perceptual abnormalities but increases the mood elevating effects. Haloperidol may decrease impairment by ketamine in executive control functions, but does not affect psychosis, perceptual changes, negative schizophrenic-like symptoms, or euphoria. Alfentanil is additive to ketamine in decreasing pain and increasing cognitive impairment. Physostigmine and 4-aminopyridine can antagonize some pharmacodynamic effects of ketamine.

Contraindications include increased intracranial pressure (ICP), glaucoma, or acute globe injury. Caution is advised in patients with cardiovascular illness, porphyria, or thyroid disorder.

Side effects typically end 30 minutes after the termination of infusion. These risks will be mitigated using the strategies described in the protection against risks and dose adjustments sections. There are no expected side effects associated with the administration of saline.

There are no known side effects associated with completing the questionnaires. There may be some mild level of fatigue associated with answering the questions.

Confidentiality risks: The risk is privacy violation via the unexpected release of protected health information contained in health records or research data or the release of randomization information. As a result, this study involves the possibility of psychological and social risks related to breach of confidentiality.

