4.1 Description of Study Design

This is a phase 1 randomized, double-blind, placebo-controlled, two-arm parallel, single-center study.

30 subjects (15 in each arm) will be accrued. Randomization lists will be sent only to the study physician administering study drug. Participant and assessor of outcome measures will be blinded. The surgeon, anesthesiologist, and the research team members conducting the follow up visits will not know which group the subjects are assigned to. Only the physician administrating the study will be aware of whether ketamine or placebo is administered, and this provider will not be a part of any outcome measure data collection. The investigators conducting and reviewing the outcome measures will be blinded.

Adult women, aged 18-65, with chronic pelvic pain (defined as moderate to severe self-report > 6 months) will be screened for eligibility to participate in this study. Prospective subjects will be recruited, screened, and consented prior to surgery. On the day of the surgery, Eligible subjects will be randomized to one of the two groups in a 1:1 ratio to receive either intravenously (IV) ketamine (0.6 mg/kg) or matching equal dose of placebo. Subjects will receive either the study drug or placebo while recovering in the post anesthesia care unit (PACU) on the day of the surgery after subject has been deemed to be stable

May 2, 2022 Version: 1.23

2, 2022 Page 9

(hemodynamically stable, awake). The study drug or placebo will be administered by study physicians who are anesthesiologists. The study physician will administer the study intervention via an intravenous pump to deliver 0.6 mg/kg ketamine or equal volume saline over at least 30 minutes.

Participation in the study will not alter the subject's surgical or anesthetic care, post-anesthetic care, or standard of care on the floor. All subjects will also receive standard post-anesthetic monitoring and care, as well as routine care after transferring out of the PACU. There is no restriction on the use of other analgesics throughout this study. Subjects are followed, and endpoints (see below) are collected from subject reports as well as from medical charts (opioid use).

Patient demographics recorded include age, date of birth, race, MRN, gender, ethnicity, participant enrollment location, zip code, and disease site.

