A research team member will speak to the eligible subject during appointments at NYU Langone Gynecology locations including outpatient facilities and hospitals. The study surgeon may also talk to subjects about the study during their appointment and can refer subjects who are eligible. Surgeons may give potential participants the IRB-approved research flyer with key information document to introduce the study. Once a subject has been referred, a study team member will call the subject through the "recruitment and enrollment over the phone" strategies listed below. Should the potential subjects agree, the study team member will complete the informed consent process.

2. Recruitment and enrollment over the phone

a. The IRB-approved telephone script will be used to communicate the reason participants are being contacted. They will be asked if they are interested in participating in this specific study. Research team members will call prospective subjects or arrange a video conference session (WebEx only). The study team member will then ask pre-screening questions, and if deemed eligible, the study team member will explain the consent to the prospective subject and ask if the prospective subject has any questions before the prospective subject electronically signs. The study team will immediately destroy any information collected from subjects who are either determined to be ineligible or who are eligible but decide not to enroll in the study. If the prospective participant agrees, they will be sent a copy of the informed consent via REDCap. The prospective subject will remotely receive a link to the informed consent form, sign, and return informed consent document through REDCap.

May 2, 2022 Version: 1.23 Page 12

Once informed consent is given, the study team member will provide the prospective subjects with information regarding the next steps for participation. Consent may occur up to two months before surgery. Subjects will also be consented no less than 2 days before their surgery.

If a subject requests information regarding opting out of further recruitment for all research, subjects will be directed to contact [contact] or [name].

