- Any clinical adverse event (AE), laboratory abnormality, or other medical condition or situation occurs such that continued participation in the study would not be in the best interest of the
- The participant meets an exclusion criterion (either newly developed or not previously recognized) before surgery that precludes further study participation.

Criteria for discontinuing study intervention includes but not limited to:

- Allergic reaction thought to be related to study drug
- Uncontrolled hypertension, hypotension, or arrhythmia thought to be related to study drug
- Severe psychomimetic side effects
- Medical events/logistical reasons not related to study therapy

Study physician will be responsible for determining whether study interventions will be discontinued, based on his or her clinical judgement. In the case of cardiovascular side effects, if such side effects persist despite treatment based on PACU clinician's decisions, study drug may be discontinued. The reason for the dose discontinuation should be documented.

Psychomimetic side effects will be monitored by study and PACU physicians. Such side effects may be treated with reassurance. If participants continue to complain of anxiety or dysphoria or are agitated, pharmacologic agents (such as benzodiazepines) may be administered based on clinical judgement of PACU clinicians. If psychomimetic side effects are felt to be severe, with severe hallucinations, delusions, or agitation, study drug will be discontinued.

Additionally, in the event of any discontinuation of study intervention, with consent, participants will continue with the completion of remaining study visits.

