7.2.2 Enrollment/Baseline

Enrollment/Baseline Visit (Visit 1, Day 0)

- Review and verify inclusion/exclusion criteria
- Obtain informed consent of potential participant verified by signature on written informed consent or electronic consent
- Obtain demographics information
- Complete baseline/enrollment survey
- Identify and document endometriosis staging
- Identify and document final procedure(s) list
- Review and verify medical history, medication history, and demographic information
- VAS assessment of pelvic pain
- Subjects will complete the questionnaire packet for assessments which will include, EHP-30, GAD-7, DN-4, and MADRS guestionnaires. Opioid use and adverse events will also be assessed via subject reporting and medical record review. This will be done either in person, over the phone, or electronically via REDCap link sent to subject

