Introduce study and discuss participation	X						
Refer eligible participants to research coordinator	Χ						
Review and verify of Inclusion/Exclusion Criteria	X	X					
Informed Consent		X					
Demographics ¹		X					
Medical history and medication history	Χ	X					
Randomization and administer study intervention ketamine single-dose infusion or placebo			X				
Documentation of staging and procedures							
Participants will be asked which treatment arm they believe they have been assigned				X			
Assessment of Pelvic Pain using a Visual Analogue		X		X	X	X	X
Endometriosis Health Profile-30 (EHP-30)		X		X	X	X	X
General Anxiety Disorder-7 (GAD-7)		X		X	X	X	X
Montgomery-Asberg Depression Scale (MADRS)		X		X	X	X	X
Douleur Neuropathique 4 Questions (DN4)		X					
Opioid use and dosage assessment (medical records) and subject reports		X	X	X	X	X	X
Assessment of Adverse Events		X	X	X	X	X	X
Side Effects			X	X	X		
		1	1				

¹Demographics should be collected, includes: age/ date of birth, race, MRN, gender, ethnicity, and disease.

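### Eligibility is last verified before surgery although study drug is given after it, and exclusion 6 is not reconciled with section 4.1 on drugs given during anesthesia

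*Combined protocol and SAP*

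**What the plan says.** Section 5.2, exclusion 6, ends: "Use of lamotrigine, alfentanil, physostigmine, and 4-aminopyridine are contraindicated". It does not say whether this means regular use at entry, use during anesthesia, or both. Section 2.4.1 gives the background for one of these drugs: "Alfentanil is additive to ketamine in decreasing pain and increasing cognitive impairment".

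Section 4.1 says of care during the trial: "Participation in the study will not alter the subject's surgical or anesthetic care, post-anesthetic care, or standard of care on the floor". It adds: "There is no restriction on the use of other analgesics throughout this study". Section 7.3 has concomitant medications recorded but prohibits none.

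On timing, the baseline visit (section 7.2.2) includes "Review and verify inclusion/exclusion criteria" and also takes consent. In section 20 the row "Review and verify of Inclusion/Exclusion Criteria" is marked twice, for screening and baseline, and not for Visit 2. Section 5.4 says: "Subjects will also be consented no less than 2 days before their surgery". Sections 5 and 5.4 allow consent up to two months ahead.

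For exclusions that emerge later, section 5.7.1 lists this ground for ending participation: "The participant meets an exclusion criterion (either newly developed or not previously recognized) before surgery that precludes further study participation".

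**The concern.** The study drug is given after surgery and anesthesia, but the last point at which anyone is told to check eligibility lies before both. A drug named in exclusion 6 could be given in between, or another exclusion could be newly met, and no scheduled step would find it before dosing. For alfentanil the text also pulls two ways: section 5.2 calls its use contraindicated, section 2.4.1 describes it as adding to pain relief, and section 4.1 restricts no other analgesic.

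The stake is mainly safety: as written, the plan can dose a patient whom it describes as contraindicated. There is also an analysis consequence. Section 10.2 analyzes by intention to treat, so a patient found ineligible after randomization stays in a 30-patient comparison.

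**Working it through.** No single figure decides this point, so the sections are set in order of events.

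| Step | Section | Timing | Eligibility check |
|---|---|---|---|
| Screening | 7.2.1; 20 | Day -28 to -1 in 7.2.1; Day -60 to -2 in 20 | Yes |
| Baseline and consent | 7.2.2; 20 | Visit 1, Day 0 | Yes, the last one |
| Surgery | 4.1 | Day 1, POD 0 | None |
| Randomization | 4.1; 7.2.3 | Day 1; before or after surgery not stated | None |
| Drug ordered | 6.2 | On arrival in the PACU | None |
| Dosing | 4.1; 6.1.5 | In the PACU | Only that the patient is stable and awake |

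**Length of the gap.** By visit numbering it is Day 1 − Day 0 = 1 day. By the consent window in sections 5 and 5.4 it is at least 2 days and up to two months. Since 1 < 2, the two cannot both hold. On either reading the last check precedes surgery.

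**Medication rule.** Section 7.1.1 asks for a review of permitted and prohibited medications, but as part of the eligibility assessment, which ends at baseline. It cannot see drugs given during anesthesia. Visit 2 does have intraoperative ketamine documented, but attaches no eligibility consequence to it. No section tells the anesthesia team to avoid the listed drugs, or the study physician to look for them.

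**Newly met exclusions.** Between baseline and surgery section 5.7.1 gives a rule, but no visit is assigned to look. Between surgery and dosing there is neither that rule nor a check.

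**Frequency.** The documents give no rate. If each of 30 patients had an assumed independent probability p of meeting an exclusion in the gap, the chance of at least one would be 1 − (1 − p)^30:

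- p = 0.5%: 14%
- p = 1%: 26%
- p = 5%: 79% (expected count 30 × 0.05 = 1.5)
- p = 10%: 96% (expected count 30 × 0.10 = 3)

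The answer is set by the assumption, so it is not evidence of size.

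**Why the order of check and randomization matters.** Section 10.4 states 80% power for an effect size of 1.1 with 15 per arm (two-sided Wilcoxon rank-sum test, alpha 0.05, normal data). A simulation of 20,000 runs gives 79.7% with the exact test and 79.8% with the asymptotic one, so the figure reproduces and is not in dispute. As an illustration only, suppose k ketamine-arm patients are randomized, found ineligible, left undosed and kept under intention to treat with no drug effect:

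| k of 15 | Power at effect size 1.1 |
|---|---|
| 0 | 80% |
| 1 | 73% |
| 2 | 65% |
| 3 | 58% |

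These values ignore the replacement of withdrawn subjects that section 5.7.2 allows. They show why failures are better found before randomization, not that such failures will occur.

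**The case against.** The best defense is that exclusion 6 governs entry. Read as medication use at enrollment, it is covered by the section 7.1.1 review, and section 4.1 merely describes the care of patients already enrolled. On that reading the text is unclear rather than contradictory. This partly stands, and it is why the request is to reconcile the sections. But exclusion 6 carries no time window, and the stated reason for concern about alfentanil is its interaction with ketamine, which is given only after surgery.

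A second defense is that safeguards exist. Dosing is by study physicians who are anesthesiologists, and the patient must be stable and awake. Section 5.7.1 also allows termination for a medical condition that may jeopardize safety, a ground not limited to the time before surgery. Section 4.1 says it is eligible subjects who are randomized on the day. These are real but partial: none looks for the listed drugs, and no procedure that day establishes eligibility.

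Several stronger readings are tempting and are not supported:

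- *That alfentanil or physostigmine is given in theatre in this trial.* No section says so.
- *That the unrestricted-analgesics sentence also admits physostigmine.* The documents do not describe it as an analgesic. Only the sentence on unaltered anesthetic care, and the lack of any prohibition in section 7.3, leave it open.
- *That a new arrhythmia or confusion in the PACU would pass unnoticed.* The stability condition and the safety grounds in section 5.7.1 cover this in part. Exclusion 6 speaks of a history of arrhythmia, and exclusion 1 is qualified by interference with adherence or safety.
- *That the POD 1 pain comparison is biased.* The anesthesiologist is blinded (section 4.1), so drugs given in theatre should not depend on arm and should balance in expectation. Section 2.4.1 puts the general effects of a single bolus at 30 to 45 minutes, and nothing says that the interaction lasts to POD 1.

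**Conclusion.** The concern holds as a gap in procedure and an unreconciled rule. Eligibility is last verified at baseline, dosing follows surgery, Visit 2 has no check, and the rule on newly met exclusions stops short of dosing. Exclusion 6 and section 4.1 do not settle whether drugs given during anesthesia count.

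The gap is 2 days to two months by the consent window, or 1 day by the visit numbering. How many patients would be affected is unknown from the documents, and no effect on the treatment comparison has been shown. The conclusion rests on the text alone and needs no assumed rate. It should be fixed because a stated contraindication has no step to detect a breach; the unknown frequency and the partial safeguards keep it below must-fix.

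**What to change.** 1. Add a re-verification of the inclusion and exclusion criteria at Visit 2, in section 7.2.3 and as a mark in section 20, using records already reviewed that day.
2. State whether randomization takes place before or after surgery. Preferably place it after this check, so that patients who fail are not randomized.
3. In section 5.7.1, extend the rule on newly met exclusions so that it runs until study drug administration. Tying it to randomization instead could shorten it if randomization precedes surgery.
4. Reconcile exclusion 6 with the two sentences in section 4.1, saying whether it covers drugs given during anesthesia. Which clinical rule stands is for the sponsor and investigators.
5. Reconcile the Day 0/Day 1 numbering with the consent window, and state how a patient who meets an exclusion after randomization is handled under intention to treat.

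The cost is protocol wording and one checklist at an existing visit. The downside is that a few consented patients may become screen failures. Section 5.6 expects about 50 enrolled to keep 30, a margin of 50 − 30 = 20. That margin must also cover dropout, but it can absorb a few such cases.
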